Appendix D7.1 – Secondary outcome results (binary)

	Mifepristone + Misoprostol (N=)	Placebo + Misoprostol (N=)	Adjusted risk ratio ¹ (95% CI)	P-value
Key secondary outcome:				
Surgical intervention to resolve the miscarriage up to discharge from EPU				
Yes ²	N (%)	N (%)		
No	N (%)	N (%)		
Missing	N	N		
Reason for surgery				
Pregnancy tissue remaining	N (%)	N (%)		
Significant bleeding	N (%)	N (%)		
Other	N (%)	N (%)		
Missing	N (%)	N (%)		
Outcome of surgery				
Complicated	N (%)	N (%)		
Bleeding at surgery	N (%)	N (%)		
Uterine damage	N (%)	N (%)		
Need for extensive surgical intervention	N (%)	N (%)		
Other	N (%)	N (%)		
Missing	N (%)	N (%)		
Uncomplicated	N (%)	N (%)		
Missing	N (%)	N (%)		
Other secondary outcomes				
Surgical intervention to resolve the miscarriage up to and including day 7 post randomisation				
Yes ²	N (%)	N (%)		
No	N (%)	N (%)		
Missing	N	N		
Surgical intervention to resolve the miscarriage after day 7 and up to discharge from EPU				
Yes ²	N (%)	N (%)		
No	N (%)	N (%)		
Missing	N	N		
Need for further doses of misoprostol within 7 days after randomisation				
Yes ²	N (%)	N (%)		
No	N (%)	N (%)		
Missing	N	N		
Need for further doses of misoprostol up to discharge from EPU care				
Yes ²	N (%)	N (%)		
No	N (%)	N (%)		
Missing	N	N		
Infection requiring outpatient antibiotic treatment				
Yes ²	N (%)	N (%)		
No	N (%)	N (%)		
Missing	N	N		
Infection requiring inpatient antibiotic treatment				
Yes ²	N (%)	N (%)		
No	N (%)	N (%)		
Missing	N	N		
Negative pregnancy test result 21 days (± 2 days) after randomisation				
Yes ²	N (%)	N (%)		
No	N (%)	N (%)		

MifeMiso Statistical Analysis Plan v1.0

	Mifepristone + Misoprostol (N=)	Placebo + Misoprostol (N=)	Adjusted risk ratio¹ (95% CI)	P-value
Test not provided	N	N		
Missing	N	N		

¹Value <1 favours MifeMiso combination group. The risk ratio was adjusted for minimisation variables: maternal age, body mass index, previous parity, gestational age and amount of bleeding. The clustering effect of randomising centres was accounted for by using robust standard errors at centre level.

²“Yes” means the corresponding outcome measure is true.

Note: All figures presented are N (%) unless otherwise specified.

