Before the current NICE guideline CG154² was published in 2012, common practice was to use a combination of mifepristone and misoprostol (MifeMiso combination). The 2012 NICE guideline, however, recommended that misoprostol alone should be given to women having medical management². This recommendation was based on very limited evidence from one study of 115 women⁴, which found no difference between MifeMiso combination and misoprostol alone. Recognising the limited available evidence, the NICE guideline and HTA have called for a trial. In addition, the necessity of conducting such a trial was also supported by an unpublished patient survey (171/188 women thought worthwhile) and a clinician survey (120/152 of health professionals believe that a trial is necessary) at UK national level.

3. Trial objectives

Primary clinical objective: to test the hypothesis that treatment with mifepristone plus misoprostol is superior to misoprostol alone for the resolution of miscarriage within 7 days in women diagnosed with missed miscarriage by pelvic ultrasound scan in the first 13+6 weeks of pregnancy.

Key secondary objective:

To test the hypothesis that the addition of mifepristone reduces the need for surgical intervention to resolve the miscarriage.

Other secondary objectives:

1. To evaluate if the addition of mifepristone reduces the need for further doses of misoprostol.
2. To evaluate if the addition of mifepristone improves other clinical outcomes including surgical intervention up to and including 7 days post-randomisation and after 7 days post-randomisation, duration of bleeding, infection, negative pregnancy test at 21 days post-randomisation, time from randomisation to discharge from EPU care, side effects and complications.
3. To evaluate if the addition of mifepristone improves patient satisfaction
4. To assess the cost-effectiveness of the combination of mifepristone and misoprostol in the medical management of missed miscarriage.

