At least one of the time differences calculated above should be greater than or equal to 2, should be taken on or before the date of discharge from EPU care, and should not be the first dose to warrant a YES to the outcome measure.

- **Overall patient satisfaction score (measured using CSQ-8 questionnaire and collected upon discharge from EPU care)**

The outcome will be defined using a validated eight item client satisfaction questionnaire (CSQ-8)⁹. The CSQ-8 is a widely used instrument for assessing client satisfaction with health and human services, and has been used in previous trials of treatment for miscarriage¹⁰. The CSQ-8 is a brief, standardized measure of client satisfaction that is comprised of eight items. Each item asks respondents to provide their opinion and conclusions about services they have received. Each question is scored out of four. The overall score is produced by summing all item responses, with total scores ranging from 8-32 points, with higher scores indicating higher levels of satisfaction.

- **Duration of bleeding reported by woman (days) (collected up to discharge from EPU care)**

Reported on Section F (clinical outcomes until discharge) on the Outcomes form by answering "Date woman reported that bleeding started" and "Date woman reported that bleeding stopped", where days of bleeding will be computed from:

Date woman reported that bleeding stopped - Date woman reported that bleeding started.

This outcome will be treated as continuous.

- **Diagnosis of infection associated with miscarriage requiring outpatient antibiotic treatment (collected up to discharge from EPU care)**

Reported on Section F (clinical outcomes until discharge) on the Outcomes form by answering YES consecutively to the following three questions:

- a) Was the woman diagnosed with an infection that was associated with miscarriage?
- b) Were they treated as an outpatient?
- c) Was the woman prescribed antibiotics for the infection?

A binary outcome will be defined based on whether or not the above three conditions were satisfied simultaneously. If any are missing then the outcome will be coded as MISSING.

- **Diagnosis of infection associated with miscarriage requiring inpatient antibiotic treatment (collected up to discharge from EPU care)**

Reported on Section F (clinical outcomes until discharge) on the Outcomes Form by answering YES consecutively to the following three questions:

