- a) Was the woman diagnosed with an infection that was associated with miscarriage?
- b) Were they treated as an inpatient?
- c) Was the woman prescribed antibiotics for the infection?

A binary outcome will be defined based on whether or not the above three conditions were satisfied simultaneously. If any are missing then the outcome will be coded as MISSING.

- **Negative pregnancy test result 21 days (\pm 2 days) after randomisation**

Reported on Section D (pregnancy test result) on the Outcomes form by answering YES to the question "Did the woman provide a pregnancy test result?" with a negative test result. A binary outcome will be defined based on whether the test result is positive or negative and a missing value will be taken if either the woman did not provide a pregnancy test result or the result is missing.

- **Time from randomisation to discharge from EPU care (described using summary statistics only)**

Reported on Section F (clinical outcomes until discharge) on the Outcomes form by answering the question "Date of final discharge from EPU care following a negative pregnancy test", and by calculating:

Date of final discharge from EPU care following a negative pregnancy test - Date of randomisation.

- **Blood transfusion required (collected up to discharge from EPU care)**

Reported on Section F (clinical outcomes until discharge) on the Outcomes form by answering the question "Did the woman require a blood transfusion from randomisation up until discharge from EPU care?" A binary variable will be defined. If a woman withdrew or was lost to follow up before being discharged, the binary outcome will take missing values.

- **Side effects (collected up to discharge from EPU care)**

Reported on the AE form AEs that are specified with a severity grade of 3, 4, or 5, from the first administration of trial treatment until discharge from EPU care. Events will be reported based on CTCAE category¹².

A binary outcome will be derived if a woman has at least one AE.

- **Death (collected up to discharge from EPU care)**

Reported on the SAE form.

- **Any serious complications (collected up to discharge from EPU care)**

Reported on the SAE form from the first administration of trial treatment until discharge from EPU care.

A binary outcome will be derived if a woman has at least one SAE.

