Appendix C – Schedule of assessments

Outcome assessed	When?	How?	By whom?	Protocol driven (PD) or Standard Practice (SP)
Baseline data: EQ-5D-5L questionnaire	Day 0	Face to face clinical appointment with participant	Self-administered questionnaire	PD
OA1: Clinical review	Day 4-5	Telephonic or face to face clinical appointment with participant	Local research nurse/midwife or doctor	SP and PD
OA2: Clinical review +/- pelvic ultrasound, to determine whether the gestation sac has been expelled.	Day 6-7	Face to face clinical appointment with participant	Local research nurse/midwife or doctor	PD (and SP in some hospitals depending on trust policy)
OA2: EQ-5D-5L questionnaire	Day 6-7	Face to face clinical appointment with participant	Self-administered questionnaire	PD
OA3: Pregnancy test	Day 21± 2 days (point of discharge for women with negative pregnancy test result)	Clinical records and/or telephonic interview or face to face clinical appointment with participant	Local research nurse/midwife or doctor	SP
OA3: EQ-5D-5L questionnaire	Day 21± 2 days (point of discharge for women with negative pregnancy test result)	Telephonic or face to face clinical appointment with participant	Self-administered questionnaire	PD
OA4: Final discharge	Upon discharge	From clinical records or interview with the participant	Local research nurse/midwife or doctor	SP
OA4: EQ-5D-5L questionnaire (if initial positive pregnancy test result) and patient satisfaction survey	Upon discharge	Telephonic or face to face clinical appointment with participant	Self-administered questionnaires	PD
OA4: Semi-structured qualitative interview	Within 6 weeks of discharge	Face to face, via telephone or via video call with participant	Qualitative/mixed-methods researcher	PD

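### The direction-of-benefit footnotes in SAP Appendices D7.1 and D7.2 are inverted for two rows: the negative pregnancy test and CSQ-8 satisfaction

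*SAP*

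**What the plan says.** Section 9.6 of the SAP names Appendix D7.1 as a reporting template for the binary secondary outcomes and D7.2 as the template for the continuous ones.

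**D7.1.** The table has eight outcomes: three on surgery, two on further misoprostol, two on infection, and "Negative pregnancy test result 21 days (± 2 days) after randomisation". Footnote 1 sits on the risk-ratio column and so governs every row. It first says that a value below 1 favours the combination group, then continues "The risk ratio was adjusted for minimisation variables" and lists the covariates. Footnote 2 fixes the coding for every row: Yes "means the corresponding outcome measure is true".

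**Derivation of the pregnancy test outcome.** Section 9.4 bases it on a woman having provided a test "with a negative test result. A binary outcome will be defined based on whether the test result is positive or negative".

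**Which result is wanted.** Section 3 lists "negative pregnancy test at 21 days post-randomisation" among the clinical outcomes that mifepristone may improve. Appendix C describes day 21 ± 2 as the "point of discharge for women with negative pregnancy test result".

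**D7.2.** Footnote 1 is attached to the adjusted mean difference and says that a value below 0 favours the combination. The rows are CSQ-8, duration of bleeding and time to discharge. Time to discharge is summarised descriptively only. Section 9.4 defines CSQ-8 as a sum of eight items, "with total scores ranging from 8-32 points, with higher scores indicating higher levels of satisfaction".

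**The concern.** Each table gives one reading rule for a set of outcomes that do not all run in the same direction. In D7.1 the rule assumes that every Yes is a bad event, and a negative pregnancy test is a good one. In D7.2 the rule assumes that lower is better, and for CSQ-8 higher is better.

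The second and third of the other secondary objectives in section 3 ask whether mifepristone improves these outcomes. Under sections 5.1 and 5.2 they are reported with confidence intervals but without p-values, so a reader relies on which side of the null the estimate and its interval lie. That is what the footnotes misdescribe. The SAP introduction says that the reported results will follow the strategy it sets out and that deviations must be justified. The footnotes are therefore the plan's stated reading rule for these tables.

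**Working it through.** The SAP gives no expected rate for the pregnancy test and no expected CSQ-8 difference, so it has no figure of its own to reproduce here. The check compares the direction of each row with its footnote.

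**Orientation of the contrasts.** The D8 footnote gives the risk ratio as the combination relative to misoprostol alone. D6 agrees, because it says that a value below 1 for failure to pass the sac favours the combination. So RR = p(combination) / p(misoprostol alone). D7.2 does not state the order of subtraction. Its below-0 rule makes sense for bleeding only if the difference is combination minus misoprostol alone, and that order is assumed below.

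| Row | Yes or a higher value means | Favours the combination | Footnote says | Correct? |
|---|---|---|---|---|
| D7.1 surgery (3 rows) | unfavourable event | RR < 1 | RR < 1 | yes |
| D7.1 further misoprostol (2 rows) | unfavourable event | RR < 1 | RR < 1 | yes |
| D7.1 infection (2 rows) | unfavourable event | RR < 1 | RR < 1 | yes |
| D7.1 negative pregnancy test | favourable event | RR > 1 | RR < 1 | **no** |
| D7.2 duration of bleeding | longer bleeding | difference < 0 | difference < 0 | yes |
| D7.2 CSQ-8 | greater satisfaction | difference > 0 | difference < 0 | **no** |

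One of the eight binary outcomes and one of the two modelled continuous outcomes are mislabelled.

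**Does the result depend on orientation?** No. If the ratio were inverted, the negative-test row would become right and the seven other rows wrong. If the subtraction were reversed, CSQ-8 would become right and bleeding wrong. No single rule can serve either table.

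**Is there reverse coding elsewhere?** Sections 9.4 and 9.6 contain none for either outcome, and neither table makes an exception for a row.

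**Illustration.** All rates are assumed. Each line is a benefit of the combination on the negative test.

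| Misoprostol alone | Combination | RR of a negative test |
|---|---|---|
| 70% | 80% | 0.80/0.70 = 1.14 |
| 75% | 85% | 0.85/0.75 = 1.13 |
| 60% | 70% | 0.70/0.60 = 1.17 |
| 85% | 90% | 0.90/0.85 = 1.06 |

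Every ratio is above 1, so the D7.1 footnote would read each as favouring misoprostol alone. In the same way, a CSQ-8 difference of +1 point would be read as favouring misoprostol alone.

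**Other templates.** The footnotes in D6, D8 and D9.1 concern unfavourable events and point the right way.

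**The case against.** The best defence is that these are footnotes in blank tables. The outcome definitions, the models, the estimates and the confidence intervals do not depend on them. The same tables print counts and percentages of Yes by arm, with Yes defined, and means and medians by arm. A reader who saw 80% against 70% negative tests would see which arm did better. Section 5.2 treats both outcomes as exploratory, and no test or decision rule uses the labels. All of this stands, and it limits the size of the point.

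A reader might go further and infer that a real benefit would be reported as harm, or that the sign of the result would be reversed. The SAP does not support that. A risk ratio of 1.14 would still be printed as 1.14 with its proper interval, and only the note saying whom it favours would be wrong.

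The defence does not remove the error. Nothing in the SAP recodes either outcome, and no choice of orientation makes one footnote fit all its rows.

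**Conclusion.** The footnotes are wrong as written for two rows. In D7.1 the below-1 rule is inverted for the negative pregnancy test, and in D7.2 the below-0 rule is inverted for CSQ-8. This is an inconsistency between the reporting templates and the SAP's own outcome definitions. It is not a fault in the choice of analysis.

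The consequence is confined to how two exploratory secondary outcomes are labelled if the templates are used literally. The primary, key secondary and safety results are not touched.

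The conclusion rests on two readings, both supported by the SAP: that a negative test is the desired result (section 3 and Appendix C), and that a higher CSQ-8 score is better (section 9.4). The assumed rates only illustrate the mislabelling and do not measure its effect.

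**What to change.** Keep both outcomes as defined and give the affected rows their own footnotes.

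- **D7.1:** for the negative pregnancy test row, state that a risk ratio above 1 favours the combination. Keep the below-1 rule for the other seven outcomes.
- **D7.2:** state that the difference is combination minus misoprostol alone. For CSQ-8, say that a value above 0 favours the combination. Apply the below-0 rule to duration of bleeding only.

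Recoding the row as a positive test would also make the below-1 rule fit, but it is not a wording change. It would replace an outcome that sections 3, 4.4, 9.4 and 9.6 all name as a negative test, and it would change the estimate. At the assumed 80% against 70%, the ratio goes from 1.14 to 0.20/0.30 = 0.67, which is not the reciprocal of 1.14 (0.70/0.80 = 0.875).

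The cost is a few lines of template wording. No derivation, model or sample size changes.

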Appendix D7.2 – Secondary outcomes (continuous)

	Mifepristone + Misoprostol (N=)	Placebo + Misoprostol (N=)	Adjusted Mean Difference¹ (95% CI)
Overall patient satisfaction score (CSQ-8)			
Mean (SD, N)			
Median [IQR]			
Duration of bleeding reported by woman (days)			
Mean (SD, N)			
Median [IQR]			
Time from randomisation to discharge from EPU care (days)			
Mean (SD, N)			
Median [IQR]			

¹Value <0 favours MifeMiso combination treatment; adjusted for minimisation variables: maternal age, body mass index, previous parity, gestational age and amount of bleeding. The clustering effect of randomising centres was accounted for by using robust standard errors at centre level.

Appendix D7.3 – Concomitant medication post-randomisation

	Mifepristone + Misoprostol (N=)	Placebo + Misoprostol (N=)
Concomitant medication		
<Drug name 1>	N (%)	N (%)
<Drug name 2>	N (%)	N (%)
<Drug name 3>	N (%)	N (%)
<Drug name>	N (%)	N (%)

Appendix D8 – Subgroup analysis of the primary outcome

		Mifepristone + Misoprostol (N=)	Placebo + Misoprostol (N=)	Risk ratio (95% CI) ¹	P-value for interaction
Subgroups of special interest					
Gestational age (days)					
Gestational age <70	Yes ²	N (%)	N (%)		
	No	N (%)	N (%)		
Gestational age ≥70	Yes ²	N (%)	N (%)		
	No	N (%)	N (%)		
Exploratory subgroups					
Maternal age (years)					
Maternal age <30	Yes ²	N (%)	N (%)		
	No	N (%)	N (%)		
Maternal age ≥ 30	Yes ²	N (%)	N (%)		
	No	N (%)	N (%)		
Body mass index (BMI) (kg/m ²)					
BMI <35	Yes ²	N (%)	N (%)		
	No	N (%)	N (%)		
BMI ≥35	Yes ²	N (%)	N (%)		
	No	N (%)	N (%)		
Previous parity					
Nulliparous	Yes ²	N (%)	N (%)		
	No	N (%)	N (%)		
Parous	Yes ²	N (%)	N (%)		
	No	N (%)	N (%)		
Amount of bleeding					
PBAC score ≤2	Yes ²	N (%)	N (%)		
	No	N (%)	N (%)		
PBAC score ≥3	Yes ²	N (%)	N (%)		
	No	N (%)	N (%)		

¹The risk ratios between MifeMiso combination group and Misoprostol alone group, 95% confidence intervals (CIs) and the corresponding p values were estimated from log-binomial regression models, after adjustment for the minimisation variables including maternal age, body mass index, previous parity, gestational age, amount of bleeding and the interaction effect between treatment and the corresponding subgroup covariate. The clustering effect of randomising centres was accounted for by using robust standard errors at centre level. Where appropriate, the main effects of minimisation variables including maternal age, body mass index and gestational age would be treated as continuous. Risk ratios <1 favors MifeMiso combination group.

²“Yes” means failed to pass the gestational sac spontaneously within 7 days after randomisation.

Figure 3: Forest plot for subgroup analyses

Appendix D9.1 – Safety outcomes

	Mifepristone + Misoprostol (N=)	Placebo + Misoprostol (N=)	Adjusted risk ratio ¹ (95% CI)	P-value
Blood transfusion required²				
Yes	N (%)	N (%)		
No	N (%)	N (%)		
Any side effects (AEs)^{2,3}				
Yes	N (%)	N (%)		
No	N (%)	N (%)		
Side effect 1²				
Yes	N (%)	N (%)		
No	N (%)	N (%)		
Side effect 2²				
Yes	N (%)	N (%)		
No	N (%)	N (%)		
Side effects 3²				
Yes	N (%)	N (%)		
No	N (%)	N (%)		
Side effects 4²				
Yes	N (%)	N (%)		
No	N (%)	N (%)		
Side effects 5²				
Yes	N (%)	N (%)		
No	N (%)	N (%)		
Side effects 6²				
Yes	N (%)	N (%)		
No	N (%)	N (%)		
Side effects 7²				
Yes	N (%)	N (%)		
No	N (%)	N (%)		
Side effects 8²				
Yes	N (%)	N (%)		
No	N (%)	N (%)		
Side effects 9²				
Yes	N (%)	N (%)		
No	N (%)	N (%)		
Side effects 10²				
Yes	N (%)	N (%)		
No	N (%)	N (%)		
Other side effects²				
Yes	N (%)	N (%)		
No	N (%)	N (%)		
Death³				
Yes	N (%)	N (%)		
No	N (%)	N (%)		
Any serious complications (SAEs)^{2,3}				
Yes	N (%)	N (%)		
No	N (%)	N (%)		

¹Value <1 favours MifeMiso combination group. The risk ratio was adjusted for minimisation variables: maternal age, body mass index, previous parity, gestational age and amount of bleeding. The clustering effect of randomising centres was accounted for by using robust standard errors at centre level.

²Collected up to discharge from EPU care

³Total number of women experiencing at least one AE/SAE

Appendix D9.2 – Adverse Events and Serious Adverse Events – total numbers

	Mifepristone + Misoprostol (N=)	Placebo + Misoprostol (N=)
Total number of women experiencing at least one AE –n (%)	n (%)	n (%)
Total number of AEs	n	n
Total number of women experiencing at least one SAE –n (%)	n (%)	n (%)
Total number of SAEs	n	n
Total number of women experiencing at least one SUSAR –n (%)	n (%)	n (%)
Total number of SUSARs	n	n

Appendix D9.3 – Adverse events – further details by group

	CTCAE category	Date of onset	Date resolved	Severity grade ¹	Causality	Details of event
Mifepristone + Misoprostol (N=)						
1						
2						
3						
4						
Placebo + Misoprostol (N=)						
1						
2						
3						
4						

¹ Grade 3: Severe or medically significant but not immediately life-threatening; hospitalisation or prolongation of hospitalisation indicated; disabling; limiting self-care activities of daily living (ADL); Grade 4: Life-threatening consequences; urgent intervention indicated; Grade 5: Death related to AE.

Appendix D9.4 – Serious Adverse Events – further details by group

	CTCAE category	Date of onset	Date resolved	Related to the intervention	Severity	Details of event
Mifepristone + Misoprostol (N=)						
1						
2						
3						
4						
Placebo + Misoprostol (N=)						
1						
2						
3						
4
